1.2. Schema

1.3. Schedule of Activities (SoA)

	Procedure	Pre-screening ¹	Screening ¹	Treatment															
				0	1	2	3	4	5	6	7	8	9	9a	10	11	12	13	14
Visit		0	up to 28 ±7 days prior to Day 1	1	29	57	85	113	141	169	197	204 (±1day)	225	253	281	309	337	365	28 ±7 days post last dose
Study Day (visit window ±7 days)				0	4	8	12	16	20	24	28	29	32	36	40	44	48	52	
Week																			
Screening/baseline	Informed consent	X																	
	Blood collection for eosinophils eligibility confirmation (if required) ²	X																	
	Inclusion and exclusion criteria		X																
	Demography		X																
	Full physical exam including height and weight		X																
	Medical history (includes substance usage and family history of premature CV disease CRSwNP/ECRS and asthma therapy, asthma and exacerbation history and concomitant medications)			X															
	SAE Review			X															
	History of HIV and Hep B, Hep C screen				X														
	Past and current medical conditions including cardiovascular medical history					X													
	History of systemic CS use for NP					X													
	History of NP surgery						X												

	Procedure	Pre-screening ¹	Screening ¹	Treatment																	
				0	1	2	3	4	5	6	7	8	9	9a	10	11	12	13	14	15	
Visit	Study Day (visit window ± 7 days)		up to 28 ± 7 days prior to Day 1	0	1	2	3	4	5	6	7	8	9	9a	10	11	12	13	14	15	IP DISC / EW Visit
Study Day (visit window ± 7 days)						1	29	57	85	113	141	169	197	204 (± 1 day)	225	253	281	309	337	365	28 ± 7 days post last dose
Week						0	4	8	12	16	20	24	28	29	32	36	40	44	48	52	
	Parasitic screening ³					X															
	Screening 12-lead ECG					X															
	Screening Vital signs					X															
	Assessment of endoscopic NP score ¹¹					X															
	Assessment of VAS for NP symptoms including Overall VAS ⁶					X															
	Assessment of Screening CT ⁴					X															
	Screening Laboratory assessments: Haematology (including blood eosinophils) and chemistry (including liver chemistries)					X															
	Screening Urinalysis					X															
	Urine pregnancy test (WOCBP only) ⁵					X															
	Dispense and Train in the use of eDiary ⁶					X															
	Register visit	X	X	X	X	X	X	X	X	X	X	X	X		X	X	X	X	X	X	
	Randomisation					X															
	Genetics sample ⁷														X						
Efficacy	Assessment of NP Surgery					X	X	X	X	X	X	X	X		X	X	X	X	X	X	

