A documented blood eosinophil count of over 2% in the 12 months prior to Visit 0 OR through a blood sample taken between Visit 0 and Visit 1. ALL participants must meet blood eosinophil count of over 2% by Visit 1.

Participants with peripheral blood eosinophil count over 2% to 5% must also have comorbid bronchial asthma, aspirin intolerance, or nonsteroidal anti-inflammatory drug intolerance at Visit 1 assessment in order to return for Visit 2.

5. Endoscopic bilateral NP score of at least 5 out of a maximum score of 8 (with a minimum score of 2 in each nasal cavity) assessed by the investigator

6. Participants who have had at least one of the following at Visit 1:

- previous nasal surgery for the removal of NP,
- have used at least three consecutive days of systemic corticosteroids in the previous 2 years for the treatment of NP,
- medically unsuitable or intolerant to systemic corticosteroid

7. Participants with **severe NP** symptoms defined as a nasal obstruction VAS symptom score of >5

8. Presence of symptoms of CRS as described by at least two different symptoms for at least 12 weeks prior to Visit 1, one of which should be either nasal blockage/obstruction/congestion or nasal discharge (anterior/posterior nasal drip), plus

- facial pain/pressure

and/or

- reduction or loss of smell

INFORMED CONSENT

9. Capable of giving signed informed consent which includes compliance with the requirements and restrictions listed in the informed consent form (ICF) and in this study protocol.

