8.1.3. Critical procedures performed at Screening (Visit 1)

Medical history including smoking status, history of sinusitis, NP history (including NP surgery), aspirin sensitivity, history of asthma, courses of rescue corticosteroids in the past 12 months, asthma exacerbation history in the previous 12 months, smoking history.

Therapy/Concomitant medication history, including use of mepolizumab or previous biologics in the past 12 months.

Cardiovascular medical history/risk factors (as detailed in the eCRF). This assessment must include a review of the participant responses to the cardiovascular assessment questions and height, weight, blood pressure, smoking history, medical conditions, and family history of premature cardiovascular disease.

Physical exam

Vital signs

Blood for eosinophilia entry criteria

Dispensing and training of eDiary

Nasal obstruction VAS symptom score

Overall VAS symptom score

Resting 12-lead ECG

Laboratory tests. These should include:

- Chemistry
- Haematology with differential count
- Hepatitis B Surface Antigen and hepatitis C antibody
- Urinalysis
- Urine pregnancy test- for all WOCBP
- FSH and oestradiol will be assessed to confirm menopausal state (if applicable)
- Parasitic screening (only in countries with a high-risk or in participants who have visited a high-risk country)
- Endoscopic NP score
- Baseline Cranial CT scan (to be performed at Screening or during run-in period, see SoA and SRM for details)
- Review of Inclusion/Exclusion criteria
- Review of exacerbations, SAEs

Procedures conducted as part of the participant's routine clinical management [e.g. blood eosinophil counts] and obtained prior to signing of informed consent may be utilised for screening or baseline purposes provided the procedure meets the protocol-defined criteria and has been performed within the timeframe defined in the SoA.

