9.1.1. Multiple Comparisons and Multiplicity

Multiplicity arising from the multiple secondary endpoints will be controlled using the closed testing procedure specified below for strong control of type I error. Hypotheses associated with the two primary (H_1 and H_2) and six secondary endpoints (H_3 to H_8) will be tested using a gatekeeping procedure based on the graphical approach to sequentially rejective multiple test procedures [Bretz, 2009]. The two primary hypotheses H_1 and H_2 will each be tested first and will be allocated the level α , where $\alpha = 0.05$ (two-sided). If these are both rejected at level α , the procedure then is as follows: the hypotheses H_i , $i = 3, \dots, 8$ are tested each at its local significance level α_i . If a hypothesis H_i can be rejected,

its level is reallocated to one of the other hypotheses according to the pre-specified rules represented by [Figure 1](#). The reallocation weights are updated in the reduced graph and the testing step repeated for the remaining, non-rejected hypotheses with the updated local significance levels. This possibly leads to further rejected null hypotheses with associated reallocation of the local significance levels. The procedure is repeated until no further hypothesis can be rejected. The reallocation of the local alpha levels is fully determined by the initial graph ([Figure 1](#)) and the update algorithm described by [Bretz, 2009](#).

Figure 1 Multiplicity Testing Strategy Across Primary and Secondary Endpoints

Primary:

H_1 : Total Endoscopic Nasal Polyps score at Week 52

H_2 : Nasal Obstruction VAS score during the 4 weeks prior to Week 52

Secondary:

H_3 : Overall VAS score during the 4 weeks prior to Week 52

H_4 : Lund Mackay CT score at Week 52

H_5 : Composite VAS score during the 4 weeks prior to Week 52

H_6 : SNOT-22 Total score at Week 52

H_7 : Loss of smell VAS score during the 4 weeks prior to Week 52

H_8 : Time to First Nasal Surgery or course of systemic CS for CRSwNP / ECRS up to Week 52

where ϵ reflects an infinitesimally small value, indicating the potential for alpha to be reallocated dependent on the rejection of all previous tests

For the initial graph above the resulting test procedure can be summarized as follows:

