9.4.2. Secondary Endpoint(s)

Endpoint	Statistical Analysis Methods
Secondary	
Estimands for the secondary variables of change from baseline in SNOT-22 total score at Week 52, change from baseline in mean overall VAS symptom score, mean composite VAS score (combining VAS scores for nasal obstruction, nasal discharge, mucus in the throat and loss of smell) and mean VAS for loss of smell score at Week 52 (calculated as the mean of all measurements made in the 4 weeks prior to Week 52), and change from baseline in Lund Mackay CT score at Week 52 will use the same population, summary measure and strategies for intercurrent events as for the primary estimands. Analysis methods will be the same as for the co-primary endpoints.
 
For the endpoint of time to first nasal surgery or course of systemic CS for CRSwNP / ECRS up to Week 52, the summary measure will be the hazard ratio. The anticipated intercurrent events of premature discontinuation of study treatment or changes in background medication/starting of a prohibited medication will be handled using a treatment policy strategy, such that available event times will be included in the analysis regardless of whether the event (surgery or course of systemic CS for CRSwNP / ECRS) occurred before or after discontinuation of randomised treatment or changes in background medication/starting of a prohibited medication. Data impacted by COVID-19 related intercurrent events will not be included in the statistical analyses and each subject will be censored at the time of the COVID-19 related intercurrent event. Statistical analysis will use the Cox proportional hazards model with covariates of treatment group, log of baseline blood eosinophil count, number of previous surgeries (1, 2, >2; ordinal), background INCS use and country. A graph of the Kaplan-Meier estimates of the proportion of participants with events over time will be produced by treatment group. If a participant withdraws from the study before experiencing nasal surgery or having a course of systemic CS for CRSwNP / ECRS, the event time will be censored at the time of study withdrawal.

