#### 4.3.1.4. Time to First Nasal Surgery or Course of Systemic CS for CRSwNP / ECRS

Nasal polyps surgery is defined as any procedure involving instruments with resulting incision (cutting open) and removal of the polyp tissue from the nasal cavity (polypectomy/FESS). Any procedure involving instrumentation in the nasal cavity resulting in dilatation of the nasal passage such as balloon sinuplasty, insertion of coated stents or direct injection of steroids or other medication without any removal of nasal polyps tissue does not fulfil this surgery criterion. A clinical review will be carried out prior to the unblinding of treatment codes to identify all events to be considered as part of this evaluation.

Courses of systemic CS for CRSwNP / ECRS will be collected as a concomitant medication of systemic corticosteroids (taken via the following routes: oral, intravenous or intramuscular) with a collected reason for concomitant medication of 'Nasal Polyps'.

The time to first nasal surgery or course of systemic CS for CRSwNP / ECRS will be determined as the number of days from the date of first dose of study medication to the date of first event (Nasal Surgery or Course of Systemic CS for CRSwNP / ECRS, whichever is sooner). For participants who complete to Week 52 without experiencing nasal surgery or a course of systemic CS for CRSwNP / ECRS, event times will be censored at the time of the Week 52 visit. If a participant withdraws from the study before Week 52 and before experiencing nasal surgery or having a course of systemic CS for CRSwNP / ECRS, the event time will be censored at the time of study withdrawal.

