#### **4.3.2.1. Time to First Nasal Surgery or Course of Systemic CS for CRSwNP / ECRS**

For the endpoint of time to first nasal surgery or course of systemic CS for CRSwNP / ECRS up to Week 52, the treatment effect to be estimated will be the comparison of mepolizumab 100 mg SC + SoC to placebo + SoC. The population of interest will be the entire trial population (patients meeting the study inclusion/exclusion criteria with a diagnosis of CRSwNP / ECRS) who are randomised and receiving study treatment (ITT analysis set) and the summary measure of treatment effect will be the hazard ratio (mepolizumab / placebo). The hazard ratio represents the relative probability of nasal surgery or course of systemic steroids for CRSwNP / ECRS at any time during the study.

[figure not shown]
The anticipated intercurrent events of premature discontinuation of study treatment unrelated to the COVID-19 pandemic, changes in background medication/starting of a prohibited medication unrelated to the COVID-19 pandemic or interruptions of 2 or more consecutive doses to investigational product will be handled using a treatment policy strategy, such that available event times will be included in the analysis regardless of whether the event (surgery or course of systemic CS for CRSwNP / ECRS) occurred before or after discontinuation of study treatment or changes in background medication/starting of a prohibited medication. Data occurring after intercurrent events of premature discontinuation of study treatment or changes in background medication/starting of a prohibited medication related to the COVID-19 pandemic will not be included in the statistical analyses and each participant will be censored at the time of the COVID-19 pandemic related intercurrent event. If a participant withdraws from the study before experiencing nasal surgery or having a course of systemic CS for CRSwNP / ECRS, the event time will be censored at the time of study withdrawal.

Statistical analysis will use the Cox proportional hazards model with covariates of treatment group, log of baseline blood eosinophil count, number of previous surgeries (0, 1, 2, >2; ordinal), background INCS use and country. A log(-log(survival)) plot by treatment group will be used to assess the assumption of proportional hazards.

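### The Cox model for time to first nasal surgery or systemic steroid course (H8) adjusts for surgery history but not for systemic steroid history, at a small cost in efficiency

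*Protocol*

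**What the plan says.** Protocol 9.1.1 defines H8 as "Time to First Nasal Surgery or course of systemic CS for CRSwNP / ECRS up to Week 52". SAP 4.3.1.4 dates the event as "Nasal Surgery or Course of Systemic CS for CRSwNP / ECRS, whichever is sooner", and counts a steroid course only when the recorded reason is nasal polyps.

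The SAP model is: "Statistical analysis will use the Cox proportional hazards model with covariates of treatment group, log of baseline blood eosinophil count, number of previous surgeries", with the rest of the list reading "number of previous surgeries (0, 1, 2, >2; ordinal), background INCS use and country". Protocol 9.4.2 has the same set with a different surgery coding: "number of previous surgeries (1, 2, >2; ordinal), background INCS use and country". Neither list has a term for earlier systemic CS use. Neither document gives a reason, and SAP Table 3 (changes from the protocol) is silent on it.

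Steroid history is recorded at screening in two places. The Schedule of Activities (Protocol 1.3) has "History of systemic CS use for NP". Protocol 8.1.3 asks for "courses of rescue corticosteroids in the past 12 months", placed between asthma history and asthma exacerbation history.

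Inclusion criterion 6 (Protocol 5.1) needs at least one of three things: previous polyp surgery; that participants "have used at least three consecutive days of systemic corticosteroids in the previous 2 years for the treatment of NP"; or being medically unsuitable for, or intolerant to, systemic CS. Two of the three routes require no surgery.

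**The concern.** The event has two components, and the model carries the history of only one. A participant who enters on steroid use alone and one who enters on steroid unsuitability alone both have zero previous surgeries. The surgery covariate gives them the same value, yet one would expect their chances of a steroid-course event to differ.

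The steroid component is unlikely to be marginal. Protocol 2.2 describes systemic CS as standard care for ECRS in Japan, and Protocol 4.2 justifies the composite by the importance of both kinds of event.

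Leaving a prognostic covariate out of a Cox model pulls the estimated hazard ratio towards 1 and costs some power. H8 has little to give away. It is tested only after H3 to H7 are all rejected, and the sample size rests on the co-primary endpoints alone.

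**Working it through.** **1. The plan's own figures.** The only power figures are for the co-primary endpoints, with 80 per arm (Protocol 9.2, SAP 5). With SE = SD × √(2/80) and 158 degrees of freedom:

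- NP score: SE = 1.82 × 0.1581 = 0.288; smallest significant difference 1.975 × 0.288 = 0.568; power at 1.00 by the noncentral t, 93.2%.
- Nasal obstruction VAS: SE = 3.25 × 0.1581 = 0.514; smallest significant difference 1.015; power at 2.00, 97.2%.

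These reproduce the stated 0.57, 1.01, 93.2% and 97.2%. There is no H8 figure to reproduce, so everything below is illustrative.

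**2. Events H8 would need.** Schoenfeld's formula for 1:1 allocation, two-sided 5% and 80% power (assumed): events = 4(1.960 + 0.842)² / (ln HR)².

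- HR 0.50: 31.4 / 0.480, so 66 events.
- HR 0.43: 31.4 / 0.712, so 45 events. SYNAPSE's 0.43 was for surgery alone, in a population where everyone had previous surgery, so it does not transfer directly.

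**3. Cost of leaving the term out.** Assumed: 160 participants, 1:1; true treatment HR 0.5; exponential event times censored at one year; half with steroid history; baseline hazard λ of 0.2 or 0.4 per year; history HR γ of 1.5, 2 or 3. The implied placebo one-year risk is ½[(1 − e^(−λ)) + (1 − e^(−λγ))]. Each of 700 simulated trials per row was analysed without and with a yes/no history term.

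| λ | γ | Placebo risk | Mean events | Power without → with | Median HR without → with |
|---|---|---|---|---|---|
| 0.2 | 1.5 | 22% | 27.0 | 39.7% → 41.3% | 0.492 → 0.489 |
| 0.2 | 2 | 26% | 31.7 | 43.9% → 44.6% | 0.509 → 0.506 |
| 0.2 | 3 | 32% | 39.3 | 50.4% → 55.3% | 0.514 → 0.500 |
| 0.4 | 1.5 | 39% | 48.8 | 63.6% → 63.7% | 0.498 → 0.496 |
| 0.4 | 2 | 44% | 55.5 | 67.1% → 69.4% | 0.500 → 0.494 |
| 0.4 | 3 | 51% | 66.6 | 75.0% → 78.4% | 0.533 → 0.504 |

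The Monte Carlo error of each power figure is about 2 points (√(0.25/700) = 0.019). The gains at γ = 1.5 and 2 are at or near that size.

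**4. A second simulation.** Here there were 4,000 trials per scenario, γ of 2 to 3, a placebo event rate of 35 to 50%, true HR 0.45 to 0.55 and about 8% early censoring. Adjustment gained 1 to 3 points at γ = 2 and 3 to 6 points at γ = 3. The upper end is 59.1% → 65.0% (placebo rate 50%, HR 0.55, γ = 3). One example of attenuation is a mean HR of 0.570 unadjusted against 0.546 adjusted, a difference of 0.024.

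**5. Type I error.** With true HR 1 and 1,000 trials in each of five settings (λ = 0.2 with γ = 1.5, 2, 3 and 4; λ = 0.4 with γ = 1.5), the model without the term rejected in 3.2% to 4.8% of trials. There is no inflation.

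**The case against.** The strongest reply is that nothing here is wrong. The comparison is randomised, the protocol and SAP agree on leaving the term out, any attenuation is conservative, and every model omits some plausible predictor. That stands, and it limits the point to efficiency.

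Other objections also stand in part:

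- **The model already does more than adjust for surgery.** Eosinophils, INCS use and country are in it, and country may carry some of the difference in steroid practice. Neither simulation included these covariates, so the extra gain would be smaller where they overlap with steroid history.
- **The gain rests on assumptions.** Prevalence, history HR, event rate and treatment HR appear nowhere in the documents, and at a history HR of 1.5 the gain is close to zero. Both simulations used a yes/no covariate measured without error.
- **The item in 8.1.3 is not the right variable.** It is not limited to systemic courses or to NP, so it may include asthma courses. The schedule item is NP-specific but states neither a count nor a time window, so a count of NP courses over 12 months cannot be assumed to exist.
- **The model may have few events.** The illustrative counts run from about 27 to 67, and SAP 4.1.3 already foresees convergence trouble from small countries.

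A reader might go further and infer that steroid history would isolate participants who cannot take steroids and so can hardly have that half of the event. The documents do not support this. A zero would pool them with surgery-route participants who had no recorded course. The size of the group is unknown, and Protocol 7.1.1 allows short courses as medically required, without excluding anyone. That the covariate list was carried over from SYNAPSE is likewise only an inference.

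**Conclusion.** The point holds as a modest improvement in efficiency. H8 combines two kinds of event and its model adjusts for the history of one, while an NP-specific history of the other is taken before randomisation and left unused.

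Assuming 160 participants, half with steroid history, and a history HR of 1.5 to 3, adjustment would add about 0 to 6 power points and remove about 0.01 to 0.03 of attenuation in the hazard ratio. Nearly all of that arises at the stronger history effects; at 1.5 there is almost none.

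A reader might take the omission to bias the test or make the H8 result unreliable. It does neither: the randomised comparison stays valid and false-positive rates are not raised. The differing surgery coding (the SAP has a zero category, the protocol does not, and Table 3 does not list the change) is a separate matter.

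**What to change.** Before unblinding, add prior systemic CS use for NP to the H8 Cox covariates in SAP 4.3.2.1 and Protocol 9.4.2, beside number of previous surgeries. Enter it as one term with 1 degree of freedom. Take it from the NP-specific item in the Schedule of Activities, which matches the event definition in SAP 4.3.1.4, and not from the rescue-corticosteroid item in 8.1.3. Code it as the eCRF holds it: ordinal 0, 1, ≥2 if a count is recorded, otherwise yes/no. If the sponsor prefers to leave it out, one sentence giving the reason would settle the point.

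The cost is wording, a check of what the eCRF field contains, and one more parameter in a model that may have few events. No new data collection is needed and participants are unaffected. After unblinding the same adjustment could only be post hoc.

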8.1.4. Critical procedures performed at first treatment Visit (Baseline Visit 2)

- Review eDiary compliance and retrain participant if required
- Review randomisation criteria
- Review the Endoscopic NP score recorded during Visit 1 (Screening) as rated by the central laboratory
- Vital signs
- Laboratory tests. This should include
 - Clinical Chemistry including liver chemistry
 - Haematology with differential

- Blood for baseline immunogenicity
- Urine pregnancy test - for all WOCBP

8.1.5. Critical procedures performed throughout treatment period

8.1.5.1. Daily eDiary

All to be performed daily at home, including at study visit days.

- Overall VAS symptom score
- VAS for nasal obstruction, nasal discharge, mucus in the throat, loss of smell, facial pain

8.1.5.2. (Visits 2 - 15)

- eDiary at site
 - SNOT-22 questionnaire (selected visits only)
 - ACQ-5 (for asthmatics) (selected visits only)
 - SF-36 (selected visits only)
 - WPAI-GH (selected visits only)
 - Review eDiary and retrain if required
- Assessment of nasal surgery (confirmed and waiting list)
- Assessment of systemic CS dose and duration
- Endoscopic NP score (be performed at selected visits only, refer to SoA)
- End of study cranial CT scan (V15 or IP discontinuation/Early Withdrawal Visit, – performed within the visit window and up to 14 days before study visit)
- Blood for PK (to be done only at visits and in countries indicated in the SoA)
- Genetic sample (to be done one time only in any of the visits for non-Chinese participants) as per SoA
- AE/SAE review
- Concomitant medication review
- 12-lead ECG as per SoA

- Vital signs as per SoA
- Laboratory assessments as per SoA
- Blood for immunogenicity as per SoA
- Urinalysis as per SoA
- Urine pregnancy test (for all WOCBP) as per SoA
- FSH and oestradiol will be assessed to confirm child-bearing status (following a positive urine test)

